Signs and symptoms typically develop between 28 and 36 weeks of gestation, but second trimester or postpartum onset is also common. In an illustrative series of 437 women who had 442 pregnancies complicated by the HELLP syndrome, 70 percent occurred prior to delivery. Of these patients, approximately 80 percent were diagnosed prior to 37 weeks of gestation and fewer than 3 percent developed the disease between 17 and 20 weeks of gestation ([Sibai, et al 1993](#)).

Serious maternal morbidity may be present at initial presentation or develop shortly thereafter. This includes disseminated intravascular coagulation, abruptio placentae, acute renal failure, pulmonary edema, subcapsular or intraparenchymal liver hematoma, and retinal detachment, bleeding related to thrombocytopenia is an unusual presentation ([Sibai, et al 1993](#)).

Outcome and prognosis of HELLP syndrome is associated with a variety of maternal morbidities, which can rarely result in a fatal outcome. The risk of serious morbidity

correlates with increasing severity of maternal symptoms and laboratory abnormalities ([Martin ., et al 2006](#)).

The majority of patients will show evidence of resolution of the disease process within 48 hours after delivery([ACOG 2004](#))

Differential diagnosis HELLP syndrome may occasionally be confused with other diseases complicating pregnancy: acute fatty liver of pregnancy, gastroenteritis, hepatitis, appendicitis, gallbladder disease, immune thrombocytopenia, lupus flare, antiphospholipid syndrome, hemolytic-uremic syndrome, thrombotic thrombocytopenic purpura, and nonalcoholic fatty liver disease ([Page- Girling ., 2011](#)).

Thrombotic thrombocytopenic purpura and hemolytic uremic syndrome are systemic disorders characterized by endothelial injury and the formation of small vessel platelet-rich thrombi. The resulting thrombotic microangiopathy produces microangiopathic hemolytic anemia and thrombocytopenia; presenting features may also include neurologic and/or renal abnormalities ([Scully ., et al 2012](#)).

If untreated, thrombotic thrombocytopenic purpura-hemolytic uremic syndrome in adults typically follows a progressive course in which irreversible renal failure, progressive neurologic deterioration, cardiac ischemia, and death are common outcomes ([Remuzzi ., 1987](#)).

The mortality rate prior to the use of plasma exchange was approximately 90 percent ([von ., 2002](#)).

The mainstay of treatment for most patients with thrombotic thrombocytopenic purpura-hemolytic uremic syndrome is plasma exchange, which in the context of this syndrome refers to the removal of the patient's plasma by pheresis and the replacement with donor plasma rather than another replacement fluid such as albumin ([Scully., et al 2012](#)).

Compared with the mortality rate of 90 percent prior to the use of plasma exchange, the mortality rate for patients treated with plasma exchange is 25 percent or less ([Kremer., et al 2010](#)).

Thrombotic thrombocytopenic purpura-hemolytic uremic syndrome should be considered in all pregnant women with severe thrombocytopenia, severe anemia, and elevated lactate dehydrogenase enzyme ([Stella .,et al 2009](#)).

The distinction between thrombotic thrombocytopenic purpura-hemolytic uremic syndrome and severe preeclampsia is important for therapeutic and prognostic reasons. However, the clinical and histological features are so similar that establishing the correct diagnosis is often difficult; furthermore, these disorders may occur concurrently ([Burns ., etal 2004](#)).

The diagnosis of thrombotic thrombocytopenic purpura rests on evidence of microangiopathic hemolytic anemia and thrombocytopenia in the absence of disseminated intravascular coagulation and other known causes of thrombotic microangiopathy. Highly specific diagnostic tools such as serum levels of ADAMTS13 are not routinely available for immediate clinical diagnosis. The presence of schistocytes on a blood smear is the morphologic hallmark of the disease. During the early 1970s plasma exchange was introduced as an effective treatment for TTP, making early and rapid diagnosis urgent. (*Burns ., etal 2004*)

So we are searching for the association between the quantitative assessment of schistocytes in peripheral blood smear and prognosis of patient initially diagnosed as HELLPsyndrome.

Aim of the work

Research question:

In patients who are initially diagnosed as HELLP syndrome does the quantitative assessment of schistocytes will predict deterioration of HELLP syndrome after delivery ?

Research hypothesis:

We supposed that there might be a difference in the quantitative assessment of schistocytes in peripheral blood smear between women initially diagnosed as HELLP syndrome who showed no spontaneous resolution within 48 hrs after delivery and those who showed spontaneous resolution within 48 hrs after delivery.

Aim of study:

The aim of the current study is to search for a diagnostic test which might predict microangiopathic hemolytic anemia and persistent HELLP syndrome from cases who initially diagnosed as HELLP syndrome in order to start PEX/ FFP which might decrease the maternal mortality rate at Ain Shams maternity hospital

Patients and Methods

Study Design:

- o diagnostic test accuracy. (pilot study)

Study Setting:

- o Ain Shams University Maternity Hospital from January 2015 to December 2015.
- o Intensive Care Unit , Wards, Labour ward at Ain Shams University Maternity Hospital and Hematology Unit and Clinical Pathology Unit at Ain Shams University.

Study Population:

A total of 100 women with an initial diagnosis of HELLP syndrome will be recruited in the study.

Blood sample taken within 12hrs peripartum and patients will be followed up 48hrs after delivery and subdivided in to 2 groups according to improvement or deterioration after 48hrs after delivery .

Inclusion criteria :

- o Gestational age more than 20 weeks.
- o Age from 18 to 40 years old.
- o Fulfilled criteria for the diagnosis of severe preeclampsia.
- o Fulfilled criteria for the diagnosis of HELLP syndrome.

Diagnostic criteria for severe preeclampsia(one of the following):

- Blood pressure of 160 mm Hg systolic or higher or 110 mm Hg diastolic or higher on two occasions at least 6 hours apart while the patient is on bed rest (unless antihypertensive therapy is initiated before this time).
- New onset Cerebral or visual disturbances.
- Pulmonary edema or cyanosis.
- Severe persistent epigastric or right upper-quadrant pain unresponsive to medication and not accounted for by alternative diagnosis, or both.
- Impaired liver function as indicated by abnormally elevated blood concentration of liver enzymes (to twice normal concentration).
- Thrombocytopenia (platelet count less than 100, 000 per microliter. *(ACOG., 2013)*

Diagnostic criteria for HELLP syndrome:

- Hemolysis documented by an increased LDH level and progressive anemia .
- Hepatic dysfunction documented by an LDH level >600 IU/L, elevated liver enzymes documented by AST >40 IU/L, ALT >40 IU/L, or both .
- Thrombocytopenia documented by a platelet nadir less than 150, 000 cells/mm³. Thrombocytopenia is subclassified as class one HELLP syndrome: platelet nadir \leq 50, 000 cells/mm³, class two HELLP syndrome: platelet nadir \leq 100, 000 cells/mm³, or class three HELLP syndrome: platelet nadir \leq 150, 000 cells/mm³.*(Martin ., et al 1999)* .

Anticipation of Microangiopathic Hemolytic Anemia:

Thrombotic thrombocytopenic purpura-hemolytic uremic syndrome should be considered in all pregnant women with severe thrombocytopenia, severe anemia, and elevated lactate dehydrogenase enzyme (*Stella ., et al 2009*).

Methodology:

All included women will be subjected to the following:

- o History taking and consent
- o Consent form:
 - o Patient name:
 - o Hospital number:
 - o Information to the participant:
 - o The procedure
 - 1. The results of your blood results and hospital data will be used in this clinical trial.
 - 2. An extra blood sample will be withdrawn at the time of diagnosis which is a simple procedure with no known complications.
 - 3. All your data and blood results, will saved confidentially and it will appear as a number in the results.
 - 4. The results of these investigation will not affect your management plan.

- o General, abdominal and local examination.

Laboratory test:

complete blood count, using EDTA-anticoagulated peripheral blood sample, for concentration and platelet counts.

Peripheral blood smears will be taken within 12hrs peripartum and prepared within two hours of blood collection using the EDTA-anticoagulated peripheral blood sample. The blood smear then spread, air-dried, and fixed and stained according to standard procedures with panoptical stains Romanowsky stain as reported by (*International Council for Standardization in Hematology; 1984*).

Schistocytes are fragments of red blood cells (RBCs) produced by extrinsic mechanical damage within the circulation. The detection of schistocytes is an important morphological clue to the diagnosis of thrombotic microangiopathic anemia (TMA). Reporting criteria between different laboratories, however, are not uniform, owing to variability of shape and nature of fragments, as well as subjectivity and heterogeneity in their morphological assessment. Lack of standardization may lead to inconsistency or misdiagnosis, thereby affecting treatment and clinical outcome. The Schistocyte Working Group of the

International Council for Standardization in Hematology 2012 (ICSH) has prepared specific recommendations to standardize schistocyte identification, enumeration, and reporting. They deal with the type of smear, method of counting, morphological description based on positive criteria (helmet cells, small, irregular triangular, or crescent-shaped cells, pointed projections, and lack of central pallor). A schistocyte count has a definite clinical value for the diagnosis of TMA in the absence of additional severe red cell shape abnormalities, with a confident threshold value of 1%. Automated counting of RBC fragments is also recommended by the ICSH Working Group as a useful complement to the microscope, according to the high predictive value of negative results, but worthy of further research and with limits in quantitation.

International Council for Standardization in Haematology recommendations for schistocyte counting 2012:

1. Schistocytes should be evaluated on peripheral blood smears using an optical microscope at medium magnification and estimated as a percentage after counting at least 1000 red blood cells.
2. A schistocyte count should be requested and carried out when a diagnosis of thrombotic microangiopathies caused by red cell mechanical damage is suspected, usually in patients with thrombocytopenia.
3. Schistocytes should be identified by specific positive morphological criteria. Schistocytes are always smaller than intact red cells and can have the shape of fragments with sharp angles and straight borders, small crescents, helmet cells, keratocytes, or microspherocytes*.
4. A schistocyte count should be considered clinically meaningful if schistocytes represent the main morphological red blood cells abnormality in the smear (other than signs of erythropoietic regeneration).
5. A robust morphological indication for the diagnosis of thrombotic microangiopathic anemia in adults should be recognized when the percentage of schistocytes is above 1%.
6. Fragmented red cell enumeration by automated blood cell counters should be considered a useful complement to microscopic evaluation, as it provides rapid results with a high predictive value of negative samples. A microscope check is needed for positive and macrocytic samples†.

*Microspherocytes only in the presence of other mentioned RBC shapes.

†Macrocytic samples are at risk of underestimation or absence of flag ('false negative' test) (***International Council for Standardization in Hematology 2012***).

Schistocytes counting: Schistocytes will be identified and counted on the peripheral blood smear using optical microscopy. The results of microscopic examination then will be expressed as a percentage, after counting at least 1000 RBCs in optimal areas of the film. Interpretation of the examination results had been done following the (***International Council for Standardization in Hematology, 2012***) recommendations for identification, diagnostic value, and quantitation of schistocytes.

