Association between the Quantitative Assessment of Schistocytes in Peripheral Blood Smear and Prognosis of Patient Initially Diagnosed as HELLP Syndrome

Thesis

Submitted for partial fulfillment of Master Degree in
Obstetrics & Gynecology

Presented by
[name]

M. B., B. Ch.2009

Faculty of Medicine, Ain Shams University
Work at Abu Sewair medical administration

Under the supervision of
Ass. [name] [name]

Assistant Professor of Obstetrics and Gynecology
Faculty of Medicine, Ain Shams University

Lecturer. [name]

Lecturer of Obstetrics and Gynecology
Faculty of Medicine, Ain Shams University

Lecturer. [name]

Lecturer of Clinical and Chemical Pathology
Faculty of Medicine, Ain Shams University

Faculty of Medicine
Ain Shams University

2016

*Association between the Quantitative Assessment of Schistocytes in Peripheral Blood Smear and
Prognosis of Patient Initially Diagnosed as HELLP Syndrome (Study results)*

Results

The current study was conducted at Ain Shams University Maternity Hospital during the period between January 2015 and December 2015. A total of 100 women with an initial diagnosis of HELLP syndrome were recruited in the study. Blood sample taken within 12hrs peripartum and patients followed up 48hrs after delivery and subdivided in to 2 groups according to improvement or deterioration after 48hrs after delivery . All results were collected, tabulated and statistically analyzed.

Table-4 and figures 8-10 show the initial characteristics of included women.

Table-4 Initial Characteristics of Included Women .

Age (years)	
Range	18 – 38
Mean ± SD	27.51 ± 4.98
Parity	
Range	0 – 5
Median (IQR)	1 (1 – 2)
Gestational Age (weeks)	
Range	27 – 38
Mean ± SD	34.3 ± 2.91

SD standard deviation

IQR interquartile range [central 50% of ascendingly-ordered set of data]

Data presented as range, mean \pm SD; or range, median (IQR)

Figure-8 Bar-Chart showing Maternal Age Distribution in Included Women .

[figure not shown]

Figure-9 Pie-Chart showing Parity Distribution in Included Women .

[figure not shown]

Figure-10 Bar-Chart showing Gestational Age Distribution in Included Women .

[figure not shown]

Table-5 and figures 11-18 show the initial clinical and laboratory data of included women.

Table-5 Initial Clinical and Laboratory Data in Included Women .

Initial Data	
Systolic Blood Pressure (mm Hg)	
Range	170 – 240
Median (IQR)	180 (170 – 190)
Diastolic Blood Pressure (mm Hg)	

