Figure-18 Box-Plot Chart showing Hb Concentration 48 hours Postpartum in Included Women .

Figure-19 Box-Plot Chart showing Platelet Count 48 hours

Postpartum in Included Women .

Figure-20 Box-Plot Chart showing Liver Transaminases 48 hours Postpartum in Included Women .

Association between the Quantitative Assessment of Schistocytes in Peripheral Blood Smear and Prognosis of Patient Initially Diagnosed as HELLP Syndrome (Study results)

[figure not shown]
[figure not shown]

Figure-21 Box-Plot Chart showing Serum Bilirubin and

Creatinine 48 hours Postpartum in Included Women .

Of the included 100 women, 25 (25%) women showed clinical and laboratory deterioration 48 hours postpartum. All women who deteriorated postpartum received plasma exchange. Of the included 100 women, 3 (3%) died (table-7, figures 22-23).

Table-7 Postpartum Deterioration and Mortality in Included Women .

Postpartum Deterioration	
Yes	25 (25%)
No	75 (75%)
Received Plasma Exchange-steroids	
Yes	25 (25%)
No	75 (75%)
Maternal Mortality	
Yes	3 (3%)

No	97 (100%)
----	-----------

Data presented as number (percentage)

Figure-22 Pie-Chart showing Postpartum Deterioration in Included Women .

[figure not shown]
[figure not shown]

Figure-23 Pie-Chart showing Maternal Mortality in Included Wome .

There were no significant differences between women who deteriorated postpartum and women who did not regarding age, parity or gestational age (table-8, figures 24-26).

Table-8 Difference between Women who Deteriorated Postpartum and Women who did not regarding Initial Characteristics .

	Women who Deteriorated Postpartum (n=25)	Women who Did not Deteriorate Postpartum (n=75)	P
Age (years)			
Range	18 – 35	18 – 38	0.621*
Mean \pm SD	27.08 \pm 4.58	27.65 \pm 5.13	NS
Parity			
Range	1 – 4	0 – 5	0.972**
Median (IQR)	1 (1 – 2)	1 (1 – 2)	NS
Gestational Age (weeks)			
Range	27 – 38	27 – 38	0.407*
Mean \pm SD	33.88 \pm 3.14	34.44 \pm 2.83	NS

SD standard deviation

IQR interquartile range [central 50% of ascendingly-ordered set of data]

[figure not shown]
Data presented as range, mean \pm SD; or range, median (IQR)

* Analysis using Independent Student's t-test

** Analysis using Mann-Whitney's U-Test

NS non-significant

Figure-24 Box-Plot Chart showing Difference between Women who Deteriorated Postpartum and Women who did

not regarding Maternal Age .

Figure-25 Box-Plot Chart showing Difference between Women who Deteriorated Postpartum and Women who did not regarding Parity .

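### Maternal mortality is analysed as a predicted outcome, but the only stated follow-up ends 48 h after delivery and no mortality window is given

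*Protocol*

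**What the plan says.** **Follow-up.** Under Study Population the Protocol states that "patients will be followed up 48hrs after delivery and subdivided in to 2 groups according to improvement or deterioration". The Results text in the SAP says the same: "patients followed up 48hrs after delivery and subdivided in to 2 groups". Neither document describes a later contact, a discharge check or a vital-status check.

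**Target condition.** The Research hypothesis compares women "who showed no spontaneous resolution within 48 hrs after delivery and those who showed spontaneous resolution within 48 hrs after delivery". Deterioration is therefore a 48-hour state, and the SAP reports it that way: "25 (25%) women showed clinical and laboratory deterioration 48 hours postpartum".

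**Mortality.** In the Protocol's Aim of study, mortality appears only as a hoped-for benefit of early treatment, "which might decrease the maternal mortality rate at Ain Shams maternity hospital". It is not defined as an outcome. The SAP nevertheless reports that "Of the included 100 women, 3 (3%) died" and goes on to analyse death in Table-7 (3 deaths, 97 survivors), Table-11 (schistocytes by survival), Figure-39 (AUC 0.985) and Table-14 (accuracy at a cut-off of 8.2%). None of these gives a time of death or says how long the 97 survivors were observed.

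**The concern.** The accuracy of a test for predicting death can be interpreted only if death is counted up to a stated time, and up to the same time in everyone. Here the only time in the documents is 48 h, and the mortality tables do not say whether they use it.

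Where the deaths fall makes this more than a missing detail. All three were in women already classed as deteriorated and given plasma exchange. Those women may have stayed under observation past 48 h, while nothing in the documents looks past 48 h in the other 75. Group is also closely tied to the test under study: median schistocyte count is 5.5% in the 25 and 0.5% in the 75 (Table-10). If deaths were easier to find in one group, they were easier to find where counts are high, and the mortality AUC, sensitivity and NPV would look better than they are.

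**Working it through.** **Inputs**
- 25 women deteriorated and 75 did not; all 25 received plasma exchange (SAP, text above Table-7, and Table-7).
- 3 deaths and 97 survivors (Table-7).
- Schistocytes in the women who died: range 8.3% to 44%, median 39%. With three women the values must be 8.3, 39 and 44 (Table-11). Maximum in survivors: 39% (Table-11).
- Maximum in the 75 non-deteriorated women: 6% (Table-10).
- Number of late deaths missed among the 75: not in the documents. It is an assumption, called k.

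**Step 1. Reproduce Table-14 and the AUC.** At the 8.2% cut-off the 2×2 table is TP 3, FN 0, FP 4, TN 93.
- Sensitivity 3/3 = 100%; specificity 93/97 = 95.9%; PPV 3/7 = 42.9%; NPV 93/93 = 100%; LR+ = 1/(4/97) = 24.25. These agree with Table-14.
- AUC as a count of death–survivor pairs: the death at 44 exceeds all 97 survivors; the death at 39 ties with one, giving 96.5; the death at 8.3 exceeds the 93 survivors below the cut-off. (97 + 96.5 + 93)/(3 × 97) = 286.5/291 = 0.985, as reported.

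**Step 2. Locate the deaths.** The lowest count among the women who died (8.3%) exceeds the highest among the 75 (6%). All three deaths were therefore among the 25.

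**Step 3. Precision as reported.** The exact (Clopper–Pearson) 95% CI for 3/3 is 29% to 100%. For 0 deaths in 75, the exact two-sided 95% upper limit is 4.8%, even if every death was found.

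**Step 4. Effect of k missed deaths among the 75.** Each would have a count of 6% or less, hence below 8.2%, and would be a false negative. Sensitivity = 3/(3 + k); NPV = (93 − k)/93; specificity = (93 − k)/(97 − k).

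| k (assumed) | Sensitivity | Exact 95% CI | NPV | Specificity |
|---|---|---|---|---|
| 0 (as reported) | 100% | 29% to 100% | 100% | 95.9% |
| 1 | 75% | 19% to 99% | 98.9% | 95.8% |
| 2 | 60% | 15% to 95% | 97.8% | 95.8% |
| 3 | 50% | 12% to 88% | 96.8% | 95.7% |

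**Step 5. AUC for k = 1.** There are now 4 deaths and 96 survivors. The three known deaths contribute 96 + 95.5 + 92 = 283.5 pairs out of 4 × 96 = 384. The fourth contributes according to her count:
- below every survivor: 283.5/384 = 0.738;
- near the survivor median of 0.5%: (283.5 + 48)/384 = 0.863;
- above all 92 survivors under the cut-off: (283.5 + 92)/384 = 0.978.

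The first and last are outer bounds.

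**The case against.** **Unequal follow-up is inferred, not shown.** This stands. No passage says that the 25 were followed longer than the 75. The setting includes the intensive care unit and wards, the consent text covers hospital data for every participant, and Table-7 gives vital status for all 100. Nor is a 48-h cut-off for deaths shown. That the three deaths came after a 48-h classification and plasma exchange is a reasonable reading of the sequence, no more. What the documents do show is silence about the window.

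**A reader might infer that women who worsen after 48 h are misclassified as non-cases.** The documents do not support this. The hypothesis defines the target condition at 48 h, so later worsening is outside the definition. Nor would late cases have a predictable effect on Table-12. With three of them, sensitivity at 0.95% would move from 22/25 = 88% to 22/28 = 78.6% if all were below the cut-off, or to 25/28 = 89.3% if all were above it.

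**A reader might infer that a woman dying before 48 h belongs to neither group.** She has not resolved within 48 h, so the hypothesis already places her with the cases, and 25 + 75 accounts for all 100.

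**The clinical background favours a 48-h end point.** The Protocol says that TTP-HUS "typically follows a progressive course in which irreversible renal failure, progressive neurologic deterioration, cardiac ischemia, and death are common outcomes", but only when untreated. Of HELLP it says that most patients show resolution within 48 h of delivery and that a fatal outcome is rare. This justifies the 48-h grouping. It does not supply a horizon for the mortality analysis.

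**The size is hypothetical, and three deaths say little anyway.** Both are true. No missed death is documented, and the intervals for 3/3 and 3/4 overlap almost entirely. That weakens the mortality claim further; it does not rescue it.

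**Conclusion.** The point holds in this form: mortality accuracy is reported with no stated horizon, no ascertainment method and no times of death, in a study whose only stated follow-up is 48 h. That much rests on no assumption.

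The bias is conditional. If late deaths among the 75 were missed, Table-14 sensitivity and NPV are overstated, because every such death is a false negative at 8.2%. Assuming one, sensitivity is 75% rather than 100%, NPV 98.9% rather than 100%, and the AUC about 0.74 to 0.98 (0.86 if her count was near 0.5%) rather than 0.985. The effect on NPV is small; that on sensitivity is large because it rests on three deaths.

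The stronger reading, that deaths were in fact followed up differently by group, goes beyond the documents. The 48-h comparison of deteriorated and non-deteriorated women is not affected.

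**What to change.** 1. Keep the 48-h grouping for the main comparison and label deterioration throughout as a 48-h outcome.
2. Ascertain vital status for all 100 women from hospital records to one common point, at least hospital discharge. Discharge is a common event rather than a common time, so give the time from delivery to discharge by group.
3. Report when each of the three deaths occurred, and how many women in each group had known status at the chosen point.
4. Recompute Tables 11 and 14 and the mortality AUC on that basis, with exact intervals for the proportions. The printed upper limit for the AUC, 1.103, is above 1 and needs recomputing in any case.
5. If the record check cannot be done, relabel the mortality tables as deaths known during the admission and drop the claim that schistocyte count predicts maternal mortality.

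The cost is a chart check of 100 records, with no added visits or procedures. Some women may turn out to have unknown status; their number should be stated.

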Table-11 Difference between Women who Died and Women who Survived regarding Schistocytes Percentage .

	Women who Died (n=3)	Women who Survived (n=97)	P
Schistocytes (%) Range	8.3 – 44	0 – 39	<0.001*
Median (IQR)	39 (8.3 – 44)	0.5 (0.1 – 1.1)	HS

[figure not shown]
IQR interquartile range [central 50% of ascendingly-ordered set of data]

Data presented as range, median (IQR)

* Analysis using Mann-Whitney's U-Test

[figure not shown]
HS highly significant

Figure-36 Box-Plot Chart showing Difference between Women who Died and Women who Survived regarding Schistocytes Percentage .

Receiver operator characteristic (ROC) curve was constructed for schistocytes percentage as a predictor of postpartum deterioration in included women. The curve showed a significant predictability as denoted by the significantly large area under the curve (AUC) (figure-37).

Figure-37 ROC Curve for Schistocytes Percentage as Predictor of Postpartum Deterioration in Included Women .

AUC = 0.883, 95% CI (0.770 to 0.996), $p < 0.001$

Table-15 shows the validity of schistocytes at different cutoff values as predictor of postpartum deterioration.

Table-12 Validity of Schistocytes as Predictor of Postpartum Deterioration in Included Women .

Schistocytes	Sensitivity	Specificity	PPV	NPV	FP	FN	LR+
$\geq 0.95\%$	88%	85.3%	66.7 %	95.5 %	14.7 %	12 %	6
$\geq 1.4\%$	84%	96%	87.5 %	94.7 %	4%	16 %	21
$\geq 1.9\%$	80%	98.7%	95.2 %	93.7 %	1.3%	20 %	60

[figure not shown]
PPV positive predictive value -NPV negative predictive value

FP false positive -FN false negative-LR+ positive likelihood ratio

ROC curves were constructed for initial clinical and laboratory data as predictors of postpartum deterioration. Among all measured variables, only initial ALT, initial AST and initial total bilirubin were significant predictors of postpartum deterioration. Their AUCs, though being significantly large, were smaller than the AUC for

schistocytes; indicating that the latter is a more significant and better predictor for postpartum deterioration (figure-38).

Figure-38 ROC Curves for Initial Clinical and Laboratory Data as Predictors of Postpartum Deterioration in Included Women .

Initial SBP: AUC = 0.441, 95% CI (0.324 to 0.559), p=0.381

Initial DBP: AUC = 0.404, 95% CI (0.283 to 0.525), p=0.152

Initial Hb Concentration: AUC = 0.479, 95% CI (0.341 to 0.616), p=0.750

Initial Platelet Count: AUC = 0.429, 95% CI (0.293 to 0.564), p=0.286

Initial ALT: AUC = 0.636, 95% CI (0.484 to 0.787), p=0.043

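### The smear has two unreconciled sampling times and the initial comparator tests have none, so the AUC of 0.883 has no defined prediction horizon and the marker ranking may not be like for like

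*Protocol*

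**What the plan says.** The timing of the smear is stated four times.

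- Protocol, Methodology, consent form, item 2: "An extra blood sample will be withdrawn at the time of diagnosis which is a simple procedure with no known complications".
- Protocol, Study Population: "Blood sample taken within 12hrs peripartum and patients will be followed up 48hrs after delivery".
- Protocol, Laboratory test: "Peripheral blood smears will be taken within 12hrs peripartum and prepared within two hours of blood collection".
- SAP, opening paragraph of Results: "Blood sample taken within 12hrs peripartum and patients followed up 48hrs after delivery".

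The research question is "does the quantitative assessment of schistocytes will predict deterioration of HELLP syndrome after delivery", and women are grouped by their status 48 h after delivery.

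For the competing markers, the SAP text before Figure-38 says "ROC curves were constructed for initial clinical and laboratory data as predictors of postpartum deterioration". It then concludes from the sizes of the AUCs that schistocytes are the better predictor. The only specimen detail for any comparator is in the Protocol's Laboratory test section: "complete blood count, using EDTA-anticoagulated peripheral blood sample, for concentration and platelet counts". No draw time is given there, and neither specimen nor time is given for ALT, AST, bilirubin or creatinine.

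**The concern.** A prognostic accuracy figure describes a test taken at a stated moment relative to the outcome. Here that moment is either diagnosis or a window around delivery. These coincide only for women diagnosed inside the window. A woman diagnosed more than 12 h from delivery cannot satisfy both rules with one sample. The Protocol's own introduction makes such women plausible: it describes onset from the second trimester to after delivery, and in the series it cites "70 percent occurred prior to delivery".

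Two things are at stake. The first is what the AUC of 0.883 means, because a smear several days before the assessment and one taken after delivery answer different questions. The second is the ranking. If the smear and the initial biochemistry were drawn at different times, a difference in AUC partly reflects timing and not only the marker. The SAP reports no draw-to-delivery interval, and no analysis uses sampling time.

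**Working it through.** **1. The reported accuracy figures.** The AUC of 0.883 (95% CI 0.770 to 0.996, Figure-37) needs patient-level data and cannot be recomputed. Table-12 can be checked with 25 deteriorated and 75 non-deteriorated women:

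- Cutoff 0.95%: 22/25 and 64/75 give PPV 22/33 = 66.7%, NPV 64/67 = 95.5%, LR+ 6.
- Cutoff 1.4%: 21/25 and 72/75 give PPV 21/24 = 87.5%, NPV 72/76 = 94.7%, LR+ 21.
- Cutoff 1.9%: 20/25 and 74/75 give PPV 20/21 = 95.2%, NPV 74/79 = 93.7%, LR+ 60.

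All agree with the table. A monotone ROC curve through these three points has an area between 0.862 and 0.980, so 0.883 is compatible. The issue is what the figure measures, not its arithmetic.

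**2. Prediction horizon.** Assume, because the documents do not say, that peripartum means up to 12 h either side of delivery.

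- Latest smear: 48 − 12 = 36 h before the assessment.
- Earliest smear: 48 + 12 = 60 h before it.
- Smear at an antepartum diagnosis more than 12 h before delivery (consent rule): more than 60 h.
- Diagnosis more than 12 h after delivery: outside the window, and less than 36 h if the consent rule were followed.

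Narrower readings do not settle the matter. If the window lies only before delivery, a woman diagnosed postpartum cannot comply. If it lies only after delivery, every smear falls inside the 48-h follow-up.

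**3. How secure the ranking is.** SEs are taken from the printed intervals, as width/3.92.

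- Schistocytes: (0.996 − 0.770)/3.92 = 0.0577.
- Bilirubin: (0.887 − 0.656)/3.92 = 0.0589.
- Difference: 0.883 − 0.772 = 0.111.
- SE of difference = √(SE₁² + SE₂² − 2r·SE₁·SE₂), where r is the correlation between the two AUC estimates. The documents do not give r, so a range is shown.

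| assumed r | SE | 95% CI | p |
|---|---|---|---|
| 0 | 0.0824 | −0.051 to 0.273 | 0.18 |
| 0.3 | 0.0690 | −0.024 to 0.246 | 0.11 |
| 0.5 | 0.0583 | −0.003 to 0.225 | 0.057 |
| 0.6 | 0.0521 | 0.009 to 0.213 | 0.033 |
| 0.7 | 0.0452 | 0.022 to 0.200 | 0.014 |

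Over the same range of r, the lead over AST (0.883 − 0.694 = 0.189) has p of 0.04 or less. The lead over ALT (0.883 − 0.636 = 0.247) has p of about 0.01 or less.

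**4. Precision of a timing split.** The current half-width is (0.996 − 0.770)/2 = 0.113. Suppose, for illustration only, that 30 of the 100 women were sampled after delivery. At the overall 25% rate that stratum would hold 0.25 × 30 = 7.5 events. Its half-width, scaling by sample size alone, would be 0.113 × √(100/30) = 0.206.

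**The case against.** The conflict is lopsided. One lay sentence in the consent text stands against three consistent statements, including the one in the results. The peripartum rule is therefore the one reported as used, and no woman is shown to have been sampled outside it. That stands, but the rule itself leaves the side of delivery open, and the comparators remain undated.

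Four stronger readings are tempting, and the documents do not support them.

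- A reader might infer that the AUC mixes prediction with concurrent measurement. On the two-sided window every smear precedes the 48-h assessment by at least 36 h. The onset of deterioration is not defined, so worsening could have begun before a post-delivery smear, but nothing shows that it had.
- A reader might infer that the timing favours schistocytes. That requires the smear to be later than the comparators, which is not documented. Under the consent rule the smear is drawn at diagnosis, when liver enzymes and platelets are needed for the diagnostic criteria, so the comparison could be close to like for like. Variable lead time could also lower an AUC.
- A reader might take the cited 70% as the share of pre-delivery smears. It comes from a background series and counts time of diagnosis. Under the peripartum rule a woman diagnosed antepartum could still be sampled after delivery.
- A reader might conclude that only pre-delivery smears can be said to predict. The hypothesis concerns resolution within 48 h after delivery and does not require that.

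The like-for-like question is also weaker for haemoglobin and platelets. The blood count and the smear are both described as using EDTA blood, which suggests a shared draw without stating one.

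**Conclusion.** The concern holds as an unresolved definition of sampling time, not as a demonstrated bias. The two anchors conflict for any woman diagnosed more than 12 h from delivery, peripartum is undefined, and the biochemical comparators have no draw time. The AUC of 0.883 thus has a variable horizon: 36 to 60 h under the assumed two-sided window, and longer if the smear was drawn at an earlier antepartum diagnosis.

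The statement that schistocytes outperform the initial tests may not be like for like. It is least secure against bilirubin, where the lead of 0.111 gives p from 0.18 to 0.014 as the assumed correlation goes from 0 to 0.7, with no paired test reported. The leads over AST and ALT are firmer statistically, but they are open to the same timing question. No corrected AUC, and no direction of error, can be given without collection times.

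**What to change.** 1. State one sampling anchor, worded identically in the methods and the consent text, and say whether it means before delivery, after it, or both. Recruitment is complete, so for this cohort the report should say which rule was followed. Rewording the consent cannot change what participants were told.
2. Tabulate draw-to-delivery time for the smear and for each comparator.
3. Keep the pooled AUC and add, as a sensitivity analysis, the schistocyte AUC for smears drawn before and after delivery.
4. Compare markers on values from the same draw, or the closest draw, with a paired AUC test such as DeLong's, and report each difference with its interval.
5. If collection times were not recorded, say so and soften the wording on prediction and on being the better predictor.

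If times were recorded, the cost is a wording change, one table and a short reanalysis. The downside is imprecision in the strata. With about 30 women after delivery (an assumption) there would be roughly 7 to 8 events and a half-width near 0.21. Because 0.883 + 0.206 exceeds 1, that is only an order of magnitude, and the stratum interval should be computed by a method that respects the upper bound of 1.
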